14.1 Data Analysis Plan

Analysis plan: Continuous data will be analyzed using ANOVA with repeated measures, or student's T-Test (where applicable) in order to compare differences between the treatment and control groups. For categorical data, Fisher's Exact test to determine differences between groups. Statistical significance will be evaluated using $\alpha=0.05$.

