14.2 Sample Size

Inclusion Criteria are men with IIEF scores >11 which includes men with mild (IIEF 16-21) and mild/moderate (12-16) Erectile dysfunction. Minimal clinically important difference (MCID) for these groups are an increase of 2 for mild and 5 for moderate ED. Previous studies on the effect of placebo show about a 15% improvement in men with mild to moderate ED. Therefore, 15% of the placebo group is expected to meet MCID. Results from the PRP safety study by Matz et al. 2018, which showed a mean improvement in IIEF of 4.14 points in seven patients with ED after PRP. In the interventional group, we expect 50% to meet MCID. At 80% power, we will therefore need 30 patients in each group to detect a difference of 35% between treatment and placebo arms.

$$\text{Sample size} = \frac{2(Z_{\alpha/2} + Z_{\beta})^2 P(1-P)}{(P_1 - P_2)^2}$$

$$24 = (2*(1.96+0.84)^2 * (0.25*(1-0.25))) / (0.35^2)$$

Assuming attrition of approximately 20%, an additional 6 participant slots will be added to each group for a total sample size of 60 subjects.

15. Risks and Benefits

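### The 80% power in Section 14.2 is not what the planned Fisher's exact test delivers: it is 67% with 24 evaluable men per arm and 78% with all 30, and the P = 0.25 in the formula is unexplained.

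*Combined protocol and SAP*

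**What the plan says.** Section 14.2 sizes the trial on the proportion of men reaching the MCID. For placebo it says: "Therefore, 15% of the placebo group is expected to meet MCID". For active treatment: "In the interventional group, we expect 50% to meet MCID". The control figure is drawn from earlier placebo studies described as showing roughly a 15% improvement.

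The section prints a normal-approximation formula with a single P in the variance term and evaluates it as "24 = (2*(1.96+0.84)^2 * (0.25*(1-0.25))) / (0.35^2"). P is not defined. The enrolled number follows: "Assuming attrition of approximately 20%, an additional 6 participant slots will be added to each group for a total sample size of 60 subjects". The power claim is attached to the enrolled number: "At 80% power, we will therefore need 30 patients in each group to detect a difference of 35% between treatment and placebo arms".

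For the analysis, Section 14.1 assigns categorical data to Fisher's "Exact test to determine differences between groups", with alpha 0.05. It does not state sidedness, but the 1.96 in Section 14.2 implies a two-sided test.

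Section 4.2 lists MCID response at 3 and 6 months as a secondary endpoint. The primary endpoint in Section 4.1 is treatment-emergent serious adverse events, and no sample-size argument is given for it.

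**The concern.** Two things do not fit together. First, 0.25 is neither of the assumed rates nor their mean, so the printed calculation does not visibly use the plan's own assumptions. Second, the formula is for a normal-approximation test, while the planned test is Fisher's exact test, which is conservative in samples this small. A sample size that just reaches 80% under the approximation will fall short under Fisher.

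This matters because MCID response is the only endpoint used to justify 60 men. If the results are read as coming from an 80%-powered comparison, a non-significant result will be taken as stronger evidence against the assumed 35-point effect than it is.

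The control rate is a further, softer issue. The step from a 15% improvement to 15% of men responding is not explained, and power depends heavily on that rate.

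**Working it through.** **Inputs.** Placebo rate 0.15, active rate 0.50, z-values 1.96 and 0.84, P = 0.25 and attrition of about 20% (all Section 14.2). Alpha 0.05 and Fisher's exact test (Section 14.1). Allocation 1:1 (Section 6).

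**1. Reproduce the plan's figure.** The formula is n = 2 × (1.96 + 0.84)² × P(1 − P) / (0.35)².

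- With P = 0.25: 2 × 7.84 × 0.1875 / 0.1225 = 24.0.
- Attrition: 24 / 0.80 = 30 per arm, 60 in total.

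The printed arithmetic is correct, and so is the inflation for attrition.

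**2. The same formula with the plan's own rates.** The mean is (0.15 + 0.50)/2 = 0.325.

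- 2 × 7.84 × 0.325 × 0.675 / 0.1225 = 28.08, so 29 evaluable per arm.
- After 20% attrition: 29 / 0.80 = 36.25, so 37 per arm.

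**3. Power of the planned test.** For each n per arm, I enumerated all pairs of responder counts from two independent binomials (0.50 and 0.15). I then added the probabilities of the pairs for which two-sided Fisher gives p ≤ 0.05.

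| Evaluable per arm | Fisher power, 15% vs 50% |
|---|---|
| 24 (after 20% attrition) | 66.8% |
| 29 | 75.7% |
| 30 (no attrition) | 77.7% |
| 31 | 79.7% |
| 32 | 81.5% |

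The first n above 80% is 32 evaluable, which is 32 / 0.80 = 40 enrolled per arm. At 24 per arm, Fisher's actual type I error never exceeds about 2.9% against the nominal 5%, which accounts for the loss. For comparison, the exact power of the uncorrected chi-square test at 24 per arm is 76.7%.

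**4. Effect detectable at 24 per arm.** Against 15%, Fisher power is 79.6% at an active rate of 55.5% and 80.6% at 56%. So 80% power needs about 15% vs 56%, a gap of 41 points rather than 35.

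**5. An unconditional exact test.** With Boschloo's test at the same alpha (maximum size checked over a grid of common rates), power for 15% vs 50% is 74.7% at 24 per arm and 82.1% at 30.

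**6. Sensitivity to the control rate.** The rates above 15% below are my assumptions, not figures from the plan. Active rate 50%, Fisher, 24 per arm:

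| Control rate | Power |
|---|---|
| 15% (plan) | 67% |
| 25% | 34% |
| 30% | 21% |
| 35% | 13% |

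The active rate is held at 50%, so the gap shrinks as the control rate rises.

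**The case against.** **The number 24 can be defended.** With separate variances for the two arms, n = (1.96 + 0.84)² × (0.15 × 0.85 + 0.50 × 0.50) / 0.35² = 7.84 × 0.3775 / 0.1225 = 24.16, strictly 25. This happens because 0.25 × 0.75 = 0.1875 lies close to the mean of the two arm variances, 0.18875. A reader might infer that 24 cannot be reached from the plan's rates, or that P = 0.25 shows the plan really assumed 7.5% and 42.5%. The documents support neither inference, since P is undefined and the rates are stated as 15% and 50%. What stands is that the unpooled formula is neither the one printed nor the basis of the planned test, so it does not rescue the power claim.

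**The 67% depends on attrition.** This is fair. The power sentence names 30 per group, and with no attrition Fisher's power is 77.7%, only 2.3 points short. The honest summary is 67% to 78%, not a flat two-thirds.

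**Sidedness is not stated in Section 14.1.** A one-sided Fisher test at 0.05 would have 76.7% power at 24 and 86.2% at 30. But the plan sizes with 1.96, so a one-sided reading contradicts its own formula, and it still misses 80% at 24.

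**The endpoint is secondary and the trial is a Phase I/II pilot.** This is correct under Section 4 and limits the consequence. It does not make the stated figure right.

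**The placebo 15% may be a responder share.** It may be. The underlying studies are not identified in Section 14.2. If it is a mean score gain, 15% of a baseline of 16 to 21 (the mild range in Section 14.2) is 2.4 to 3.15 points, above the 2-point MCID given for mild ED. But 15% of 12 to 16 is 1.8 to 2.4 points, well below the 5 points given for moderate ED. A mean gain does not fix a responder rate in either case. A reader might infer that the 15% control rate is wrong; the documents show only that it is unexplained.

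**Conclusion.** The point holds. The stated 80% is not the power of the planned test, whether one counts 24 evaluable men per arm or all 30. Under the plan's own 15% and 50%, two-sided alpha 0.05 and Fisher's exact test, power is 67% with the assumed 20% attrition and 78% with none; 80% needs 32 evaluable per arm. The mismatch between sizing method and planned test is the main defect. The unexplained P is secondary: in the printed formula it moves the requirement from 24 to 29 evaluable per arm.

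Two stronger conclusions are not supported. One is that the trial is underpowered for its primary endpoint: that endpoint is safety, and the calculation does not address it. The other is that power is as low as 13% to 34%: those figures rest on assumed control rates of 25% to 35% and show only how sensitive the design is to a rate the plan does not justify.

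**What to change.** Keep N = 60 and rewrite Section 14.2.

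1. Correct P to 0.325, or define P and explain 0.25.
2. State power for the planned test. Suggested wording: *With Fisher's exact test (two-sided, alpha 0.05), power for 15% vs 50% is 67% with 24 evaluable men per arm and 78% with 30; with 24 per arm, 80% power is reached at about 15% vs 56%.*
3. Say whether the placebo 15% is a responder share on the plan's own MCID or a mean score gain. Show power over a range of control rates, labelled as assumptions, as in the sensitivity table above.
4. Optionally, prespecify Boschloo's exact test for MCID response in Section 14.1. Section 14.2 must then quote that test's power (75% at 24 per arm, 82% at 30) and not Fisher's. Fisher's test is valid, so this is a choice rather than a correction, and it does not restore 80% after the assumed attrition.

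The cost is one rewritten paragraph and a less favourable power statement, with no extra patients. The change should be made before unblinding.

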2.4 Combination Restorative Therapy for Erectile Dysfunction

The development of ED therapeutics that focus on neurovascular regeneration and repair strategies are of great importance. A large body of *pre-clinical* work has demonstrated the effect of SWT alone (monotherapy) on angiogenesis and progenitor / stem cell recruitment for ED [2, 3, 8-11]. PRP monotherapy importantly is also supported by well-defined mechanistic insights obtained from rigorously conducted animal studies [12-19]. All the previous studies in humans have evaluated either IIEF scores and / or penile Doppler ultrasound hemodynamic parameters, but there has not been evaluation of the treatment as a combination. The proposed mechanisms of both interventions would

suggest that the combination therapy would act in a synergistic manner, with superiority over monotherapy. Success of our proposed work could fundamentally change the standard of care for ED and substantially improve the quality of life for tens of millions of men.

3. Study Objectives

3.1 Primary Objective:

To investigate and compare the safety of PRP and SWT vs placebo/sham treatment in men with mild-moderate ED.

3.2 Secondary Objective:

To study the treatment efficacy of PRP and SWT treatment vs placebo/sham treatment in men with mild-moderate ED.

4. Study Endpoints

4.1 Primary Endpoint (safety):

- Incidence of treatment emergent serious adverse events (TE-SAEs) in all patients during the study period. Adverse events will be recorded at every visit. The following contains a list of the anticipated adverse events:
 - Pain
 - Bruising
 - Swelling
 - Edema
 - Allergy
 - Penile Fracture
 - New Penile Curvature

4.2 Secondary Endpoints (efficacy):

- Change in IIEF-EF score from baseline to 3 and 6 months post-therapy compared to control group.
- Percentage of subjects that achieve minimal clinically important difference (MCID) in IIEF-EF from baseline to 3 and 6 months post-therapy compared to control group,
- Percentage of subjects who either decrease or discontinue use of PDE5i after three months post-therapy compared to control group.

4.3 Exploratory Endpoints:

- Differences in Doppler ultrasound parameters (PSV and EDV) from baseline to 6 months post-therapy compared to control group.
- Treatment satisfaction as assessed by EDITS questionnaire in all subjects.
- Changes in IPSS questionnaire between treatment and control group.
- Perceptions of therapeutic allocation between treatment and control group.

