- 8.2.13 *PRP/Placebo Injection:*** Approximately 120mL of blood will be collected from participants for preparation of investigational product. Refer to Section 9.2 for description of IP preparation and administration.

8.2.14 Concomitant Medications: Review of current use of prescription and over the counter (OTC) medications. Participants must discontinue use of PDE5i medications throughout the duration of the study.

8.2.15 Review Adverse Events: Refer to Section 12 for description and reporting of adverse and serious adverse events.

8.2.16 SWT/Sham Treatment: In the treatment group, patients randomized will receive 5 weekly sessions, in which 720 shocks of treatment energy will be applied in every session to each treated region (left and right corpora cavernosa and crura). In the sham group, patients will have the same number of sessions, and the machine will be set to deliver 720 shock treatments, but the machine will not fire shockwaves.

8.2.17 Laboratory Testing: Hematology, chemistry, hemoglobin A1C, and serum testosterone lab test results will be collected at screening. If any standard of care labs testing have been performed within 12 months of the date of the screening visit, those results may be used for the purpose of this study.

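### The MCID responder comparison has no stated analysis population and no rule for a missing IIEF-EF, so by default it is run on completers, and its significance can depend on the rule chosen

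*Combined protocol and SAP*

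**What the plan says.** Section 4.2 makes this a secondary efficacy endpoint: "Percentage of subjects that achieve minimal clinically important difference (MCID) in IIEF-EF from baseline to 3 and 6 months post-therapy", compared with control. It is the only endpoint with a sample-size calculation. Section 14.2 assumes 50% responders on active treatment and, for control, "Therefore, 15% of the placebo group is expected to meet MCID". Its formula gives 24 per arm, and it then states: "Assuming attrition of approximately 20%, an additional 6 participant slots will be added to each group for a total sample size of 60 subjects".

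Section 14.1, the whole analysis plan, says of binary outcomes only: "For categorical data, Fisher's Exact test to determine differences between groups". It names no analysis population, no scoring of a man without a follow-up IIEF-EF, and no sensitivity analysis. Two other places touch on missing men. Section 10.1 asks for the reason for missing data to be documented, and Section 7.4 has withdrawn men de-enrolled from the research database. Neither says how such a man counts in the responder comparison.

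Section 6 describes the population as men who use PDE5 inhibitors regularly and respond to them. Section 8.2.14 adds: "Participants must discontinue use of PDE5i medications throughout the duration of the study".

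**The concern.** The six added men per arm replace leavers, so the planned power rests on 24 scored men per arm. With no rule for the others, a man without a score drops out of the Fisher table by default. The comparison is then no longer between the groups as randomised.

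Loss may also be related to outcome. Men who were responding to a PDE5 inhibitor must stop it, so a man without benefit may have more reason to leave. That is an inference from the protocol's own rules, not something it states. If it is right, completer responder rates are too high, most of all in the arm that loses more men. Leaving the rule unwritten also allows it to be chosen after the data are seen, when the choice can decide significance.

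**Working it through.** **Inputs.** Section 14.2 gives responder rates of 15% (control) and 50% (active), 80% power, z-values 1.96 and 0.84, P = 0.25 and attrition of about 20%. Section 14.1 gives Fisher's exact test at 0.05, taken as two-sided to match 1.96.

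**The plan's own figure.** 2 × (1.96 + 0.84)² × 0.25 × 0.75 / 0.35² = 24.0 per arm. Then 24 / 0.8 = 30 per arm, 60 in total. Both reproduce. Expected loss is 6 per arm, 12 of 60.

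**Scoring the missing men.** 50% of 24 = 12, and 15% of 24 = 3.6, rounded to 4. With 6 missing per arm:

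| Scoring of the 12 missing men | Control | Active | Fisher p |
|---|---|---|---|
| Dropped (completers) | 4/24 | 12/24 | 0.030 |
| All non-responders | 4/30 | 12/30 | 0.039 |
| One control man a responder, other 11 not | 5/30 | 12/30 | 0.084 |
| All responders | 10/30 | 18/30 | 0.069 |
| Extreme against active | 10/30 | 12/30 | 0.79 |
| Extreme for active | 4/30 | 18/30 | 0.0004 |

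There are 49 combinations of 0 to 6 missing responders in each arm: 26 are non-significant and 23 significant. In none is control ahead; the worst is 40% against 33%. If 3.6 is rounded down to 3, completers give p = 0.011, non-responder scoring 0.015, one control responder (4/30 against 12/30) 0.039, and the extreme case 0.59.

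**Uneven loss (assumed).**
- Active loses 8, control 4: completers 4/26 against 11/22, p = 0.014; non-responder scoring 4/30 against 11/30, p = 0.072.
- Control loses all 12: completers 3/18 against 15/30, p = 0.031; non-responder scoring 3/30 against 15/30, p = 0.0015; worst case a tie, 15/30 each.

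**Type I error of the completer test.** Assume no true effect and that every leaver is a non-responder. The completer rate in an arm is then r / (1 − dropout), where r is the response rate in all randomised men.

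| r | Equal 20% dropout (24 v 24) | Assumed 10% v 30% dropout (27 v 21) |
|---|---|---|
| 15% (the plan's control rate) | 2.6% | 5.0% (16.7% v 21.4%) |
| 30% (assumed) | 2.7% | 8.4% (33.3% v 42.9%) |
| 40% (assumed) | 2.9% | 11.5% (44.4% v 57.1%) |

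**Power of the named test (exact Fisher).**
- 15% v 50% on 24 per arm: 67%.
- 15% v 50% on 30 per arm, if those rates already apply to all randomised men: 78%.
- If they are completer rates and leavers count as non-responders, 0.8 × 15% = 12% and 0.8 × 50% = 40%; on 30 per arm: 62%.

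**The case against.** The plan is silent rather than wrong. Fisher's test accepts any fully scored table, and adding slots for attrition is routine and does not define an analysis set. A reader might infer that the plan prescribes a completer analysis, or that de-enrolment under Section 7.4 removes a man's data. The documents do not say so: 7.4 applies the same step to men who complete all visits. What stands is that completer analysis is the default when no rule is written.

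A reader might infer that 12 men will have no follow-up score. Section 14.2 speaks of attrition, and the Section 8.1 schedule has IIEF at both follow-up visits. A man lost after Month 3 keeps that score, so 12 is an upper figure at Month 3.

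A reader might infer that the missing men could reverse the result. At planned rates with even loss, no scoring puts control ahead. Plain non-responder scoring keeps significance. The p of 0.79 needs every missing control man to be a responder and no missing active man to be one, which sits badly with the idea that leavers are men without benefit.

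A reader might also infer inflated false-positive risk, or bias towards treatment. Under no effect in a blinded trial, leaving for lack of benefit should be about equal between arms, and the error then stays below 3%. The 8.4% and 11.5% need an assumed dropout split and response rates at least twice the documented 15%, at which the same split gives 5.0%. If treatment works, leaving for lack of benefit falls mainly on control, and dropping those men works against the treatment.

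Finally, this is a secondary endpoint in a pilot whose primary endpoint is safety. That limits the weight, although the trial is sized on this endpoint.

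**Conclusion.** The gap is real and worth closing. The endpoint that sets the sample size has no defined denominator, and at about the planned rates its significance depends on an unwritten choice: p = 0.030 in completers, 0.039 with missing men as non-responders, and 0.084 if a single missing control man is a responder. More than half of the 49 scoring combinations (26) are non-significant, so losing significance does not need the extreme case. The direction of effect is not at risk at those rates.

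These figures assume 6 missing per arm and 4 control responders among completers; with 3, one control responder among the missing is not enough to lose significance. The between-arm bias has no fixed direction, since it depends on which arm loses more men. Inflation of type I error above nominal depends on assumptions that the documents do not support. Separately, the stated 80% power is not that of Fisher's test on any of the three bases considered.

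**What to change.** In 14.1, state that the MCID comparison at each of Months 3 and 6 uses all randomised men in their assigned arm, and that a man without an IIEF-EF at that visit counts as a non-responder there. Report as sensitivity analyses the completer comparison and a tipping-point table over the number of missing men assumed to be responders in each arm (0 to 6 per arm at the planned attrition).

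In 14.2, say whether 15% and 50% refer to all randomised men or to completers, and replace 80% with the power of Fisher's test on the chosen basis: about 78% or about 62% on 30 per arm, against about 67% on 24 completers.

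The cost is a few sentences and a restated figure, with no extra patients or visits for the change itself. Stated response rates and power will be lower. Non-responder scoring is conservative for each arm's response rate, but not always for the difference: if control loses more men it can favour active treatment, which is why the tipping-point table is needed. Other rules are defensible; what matters is that one is fixed before unblinding.

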15.1 Risks to Subjects

We anticipate there to be few adverse events related to the study. Based on the four published studies and abstracts, including 75 men, only minor adverse events were reported (Bruising 1, Mild Pain 4). No serious adverse events were observed [23-26]. After literature review, we believe this product to be of non-significant risk to patients (NSR) and for investigational use in a clinical study protocol.

Based on published studies, we will record anticipated adverse events to patients include: local injection site reaction, penile pain, penile hematoma (bleeding into the tissue), penile swelling, allergic reaction to the anesthetic, local infection, penile fracture, or new penile curvature. In addition, there may be uncommon or previously unknown risks that might occur. We will record every adverse event at every visit systematically.

15.2 Potential Benefits to Subjects

The potential benefits for men randomized to the treatment arm will include improvement in erectile function and sexual performance.

16. Privacy & Confidentiality

Each subject's protected health information will remain strictly confidential and shall be excluded from the database. Patients deemed eligible to participate in the study following evaluation of inclusion/exclusion criteria will be assigned a unique study participant identifier number (ex.: COC-01). The first two characters indicate the enrolling site, next 5 characters describe the study and phase, and final 3 characters are the unique identification number assigned to subjects in sequential order.

The Investigator will retain a cross-referencing record of each subject's name and assigned identifier number. All study data and results will be stored in the electronic database. Each study subject will give explicit consent for representatives of the IRB/IEC and regulatory authorities to inspect and verify each subject's medical records and collected information. In turn, each study subject will be assured that all their personal information will be maintained in the strictest of confidence, and in compliance with HIPAA, and all other federal and local laws regulating privacy and data protection.

Data will be collected from the EMR or subjects at UHealth or JHS. Research subjects will sign a HIPAA Authorization before collection of data for this research study.

